8.1.2 Relationship Categorization

A physician/investigator must make the assessment of relationship to the IP for each AE. The investigator should decide whether, in his or her medical judgment, there is a reasonable possibility that the event may have been caused by the IP. If there is no valid reason for suggesting a relationship, then the AE should be classified as “not related”. Otherwise, if there is any valid reason, even if undetermined or untested, for suspecting a possible cause-and-effect relationship between the IP and the occurrence of the AE, then the AE should be considered “related”. The causality assessment must be documented in the source document.

The following additional guidance may be helpful:

Term	Relationship Definition
Related	The temporal relationship between the event and the administration of the IP is compelling and/or follows a known or suspected response pattern to that product, and the event cannot be explained by the subject's medical condition, other therapies, or accident.
Not Related	The event can be readily explained by other factors such as the subject's underlying medical condition, concomitant therapy, or accident and no plausible temporal or biologic relationship exists between the IP and the event.

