9.9 Safety Analyses

The Safety Analysis Set will be used to assess the safety endpoints.

Adverse events will be coded using the Medical Dictionary for Regulatory Activities. Treatment-emergent AEs are defined as AEs that start or worsen on or after the date of the first dose of IP, and no later than the follow-up visit. The number of events, incidence, and percentage of TEAEs will be calculated by SOC, by preferred term, and by treatment group. Treatment-emergent AEs will be further summarized by severity and relationship to the IP. Adverse events related to the IP, AEs leading to withdrawal, SAEs, and deaths will be similarly summarized/listed.

Vital signs, ECG findings, and clinical laboratory tests will be summarized by treatment group and visit. Potentially clinically important findings will be summarized. Graphical presentation may be used when deemed necessary.

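### In Section 8.1.2 the definition table sets a higher bar for a related AE than the text above it, and its two classes are not exhaustive

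*Protocol*

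**What the plan says.** Protocol Section 8.1.2 gives the same classification twice.

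**The text.** The investigator is to judge whether "there is a reasonable possibility that the event may have been caused by the IP". The rule for the lower class begins "If there is no valid reason for suggesting a relationship, then the AE should be classified as" not related. In every other case, "if there is any valid reason, even if undetermined or untested, for suspecting a possible cause-and-effect relationship" with the IP, the event is related. The possibility of another cause plays no part in this rule.

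**The table.** It is introduced as further guidance. An event is *Related* if its timing is "compelling and/or follows a known or suspected response pattern to that product, and the event cannot be explained by" the subject's illness, other treatment or an accident. *Not Related* has two conditions joined by *and*. The first begins "The event can be readily explained by other factors such as" the same kinds of alternative; the second is that "no plausible temporal or biologic relationship exists between the IP and the event".

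There is no third category, and no sentence says which wording governs when the two differ.

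The label is used later. Section 9.9 states "Treatment-emergent AEs will be further summarized by severity and relationship to the IP", and Section 8.2.6 makes the notification of unexpected SAEs depend on their being related.

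**The concern.** The text sets a low threshold for *related*, while the table adds a requirement that no other cause can account for the event. Many adverse events in a trial population with comorbidity and concomitant medication have some rival explanation, so the added clause matters in practice.

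The protocol itself supplies an example. Section 1.3, in the earlier protocol version at hand, reports a Phase 1 ALT increase on volixibat that became an SAE and was considered related. Every subject in this trial has NASH, and the eligibility criteria in that version exclude ALT only above 5 times ULN at screening. An ALT rise on treatment could therefore often be put down to the underlying disease as well as to the IP. The text keeps such an event related as long as there is a valid reason to suspect the IP. The table's *Related* definition may not.

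At stake is whether counts of related events mean the same thing across investigators, and whether a related, unexpected SAE is recognised as such.

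**Working it through.** The protocol gives no figure on this point, so the check is a logical one. Cross three levels of evidence for the IP with three levels of alternative explanation, and classify each of the 3 × 3 = 9 combinations by the text and by the table. The one assumption is that a plausible link counts as a valid reason to suspect the IP.

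| Evidence for the IP | Another cause readily explains the event | Another cause is possible, but not readily | No other cause can explain it |
|---|---|---|---|
| Compelling timing or response pattern | text: related; table: neither | text: related; table: neither | text: related; table: Related |
| Plausible only | text: related; table: neither | text: related; table: neither | text: related; table: neither |
| Not plausible | text: not related; table: Not Related | text: not related; table: neither | text: not related; table: neither |

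- **Text:** 6 related + 3 not related = 9. The rule is exhaustive.
- **Table:** 1 Related + 1 Not Related = 2 classified, so 9 − 2 = 7 are in neither class.
- **The 7 unclassified combinations:** 4 have a plausible or stronger link together with another possible cause (text: related); 1 is plausible only, with no other cause (text: related); 2 are not plausible and lack a ready alternative (text: not related). 4 + 1 + 2 = 7.
- **Conflict of labels:** in the 2 combinations that the table does classify, it agrees with the text. It never gives the opposite label.

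The effect on counts depends on what an investigator does with the gap:

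- If the table's *Related* definition is the only test and everything else is called not related, 1 combination is related where the text has 6. Then 6 − 1 = 5 combinations move out of *related*.
- If the table's *Not Related* definition is the only test and everything else is called related, 9 − 1 = 8 combinations are related, which is 8 − 6 = 2 more than under the text.

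These are kinds of event, not frequencies. The grid shows that the classification is ambiguous and where; it does not size the effect on any count.

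**The case against.** The strongest reply is that the text is the rule and the table is only help in applying it. The text is exhaustive and states how an event should be classified, and the table is offered as something that may assist. That is the natural reading, and it narrows the point. A reader might infer that events with a plausible link and a rival cause have no class anywhere in the protocol. That is not so: the gap is in the table alone, and the text puts them in *related*. Still, precedence is not stated, and guidance should not contradict the rule that it explains.

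The second reply is that under-calling is not inevitable. A reader might infer that anyone who follows the table will under-call. But the table's *Not Related* class also demands that no plausible link exists, so it does not allow such an event to be called not related. An investigator who reads both halves and finds neither fits should go back to the text. Under-calling needs the *Related* half to be used on its own. That could happen, but nothing in the documents shows that it will.

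Third, other provisions limit the damage. TEAEs are summarized by system organ class, preferred term and treatment group before any split by relationship (Section 9.9). Investigators report all SAEs within 24 hours whatever their cause (Section 8.2.3). Causality is judged blind, under the same wording in every arm. All of this stands, and it confines the issue mainly to the two uses in Sections 9.9 and 8.2.6.

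**Conclusion.** The point holds as a minor inconsistency in a safety classification. The text and table of Section 8.1.2 set different thresholds, the table's classes are not exhaustive, and no precedence is given. Counts of related TEAEs could differ between investigators and could be too low where the table's *Related* wording is used as the test. Recognition of related, unexpected SAEs could suffer in the same way.

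The size cannot be computed. A reader might be tempted to put a percentage on the share of gastrointestinal events affected, or to point to diarrhea in a subject who also takes metformin. The documents give no such share and do not say that metformin causes diarrhea. The permission for metformin is visible only in an earlier protocol version, where it requires a stable regimen for the 6 months before the qualifying biopsy.

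A reader might also infer that the urgent safety review is affected. The current Section 9.5.2 refers to Section 4.5.4, but the criteria there (a related death, or two similar related SAEs) can be read only in the earlier versions. That consequence is likely if the text is unchanged, but it cannot be confirmed.

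The primary endpoint, the sample size, the interim tolerability comparison (Section 9.5.1, discontinuations due to any one TEAE) and the liver stopping rules (Appendix 5) do not use relatedness and are untouched. The conclusion rests on equating a plausible link with a valid reason to suspect the IP.

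**What to change.** Either delete the table, or replace both of its definitions with the text's own rule:

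- *Related*: there is any valid reason to suspect that the IP may have caused the event, whether or not another cause is possible.
- *Not Related*: there is no such reason.

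The two classes are then complementary and exhaustive.

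Striking only the alternative-cause clause from the *Related* row would not be enough. On the grid above, *Related* would then hold 3 combinations and *Not Related* 1, which leaves 9 − 3 − 1 = 5 unclassified, including all three that are plausible only.

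The cost is a wording change in Section 8.1.2 and in the eCRF completion instructions. The one downside is that somewhat more events may be labelled related.

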8.1.3 Outcome Categorization

The outcome of AEs must be recorded during the course of the study on the eCRF. Outcomes are as follows:

- Fatal
- Not Recovered/Not Resolved
- Recovered/Resolved
- Recovered/Resolved With Sequelae
- Recovering/Resolving
- Unknown.

8.1.4 Symptoms of the Disease Under Study

Symptoms of the disease under study should not be classed as AEs as long as they are within the normal day-to-day fluctuation of the disease and are part of the efficacy data to be collected in the study; however, significant worsening of the symptoms should be recorded as an AE.

8.1.5 Clinical Laboratory and Other Safety Evaluations

A change in the value of a clinical laboratory, vital sign, or ECG assessment can represent an AE if the change is clinically relevant or if, during treatment with the IP, a shift of a parameter is observed from a normal value to an abnormal value, or a further worsening of an already abnormal value. When evaluating such changes, the extent of deviation from the reference range, the duration until return to the reference range, either while continuing treatment or after the end of treatment with the IP, and the range of variation of the respective parameter within its reference range, must be taken into consideration.

If, at the end of the treatment phase, there are abnormal clinical laboratory, vital sign, or ECG values which were not present at the pre-treatment value observed closest to the start of study treatment, further investigations should be performed until the values return to within the reference range or until a plausible explanation (eg, concomitant disease) is found for the abnormal values.

The investigator should decide, based on the above criteria and the clinical condition of a subject, whether a change in a clinical laboratory, vital sign, or ECG parameter is clinically significant and therefore represents an AE.

8.1.6 Criteria for Discontinuation of Treatment

[Appendix 5](#) provides guidelines for discontinuation of treatment based on elevated ALT, AST, TB, and associated signs and symptoms.

8.1.7 Pregnancy

All pregnancies are to be reported from the time informed consent is signed until the defined follow-up period stated in Section [7.1.4](#).

Any report of pregnancy for any female study participant (or the female partner of a male participant) must be reported within 24 hours to the Shire Global Pharmacovigilance and Risk Management Department using the Shire Investigational and Marketed Products Pregnancy Report Form. A copy of the Shire Investigational and Marketed Products Pregnancy Report Form (and any applicable follow-up reports) must also be sent to the CRO medical monitor and the Shire clinical physician using the details specified in the [Emergency Contact Information](#) section of the protocol. The pregnant female study participant must be withdrawn from the study.

Every effort should be made to gather information regarding the pregnancy outcome and condition of the infant. It is the responsibility of the investigator to obtain this information within 30 calendar days after the initial notification and approximately 30 calendar days post partum.

Pregnancy complications such as spontaneous abortion/miscarriage or congenital abnormality are considered SAEs and must be reported using the Shire Clinical Study Serious Adverse Event and Non-serious AEs Required by the Protocol Form. Note: An elective abortion is not considered an SAE.

In addition to the above, if the investigator determines that the pregnancy meets serious criteria, it must be reported as an SAE using the Shire Clinical Study Serious Adverse Event and Non-serious AEs Required by the Protocol Form as well as the Shire Investigational and Marketed Products Pregnancy Report Form. The test date of the first positive serum/urine β -HCG test or ultrasound result will determine the pregnancy onset date.

8.1.8 Abuse, Misuse, Overdose, and Medication Error

Abuse, misuse, overdose, or medication error (as defined below) must be reported to the sponsor according to the SAE reporting procedure whether or not they result in an AE/SAE as described in Section 8.2. Note: The 24-hour reporting requirement for SAEs does not apply to reports of abuse, misuse, overdose, or medication errors unless these result in an SAE.

The categories below are not mutually exclusive; the event can meet more than 1 category.

- Abuse – Persistent or sporadic intentional intake of the IP when used for a non-medical purpose (eg, to alter one's state of consciousness or get high) in a manner that may be detrimental to the individual and/or society
- Misuse – Intentional use of the IP other than as directed or indicated at any dose (Note: this includes a situation where the IP is not used as directed at the dose prescribed by the protocol)
- Overdose – Intentional or unintentional intake of a dose of an IP exceeding a pre-specified total daily dose of the product.
- Medication Error – An error made in prescribing, dispensing, administration, and/or use of an IP. For studies, medication errors are reportable to the sponsor only as defined below.

Cases of subjects missing doses of the IP are not considered reportable as medication errors.

Medication errors should be collected/reported for all products under investigation.

The administration and/or use of the unassigned treatment is/are always reportable as a medication error.

The administration and/or use of an expired IP should be considered as a reportable medication error.

8.2 Serious Adverse Event Procedures

8.2.1 Reference Safety Information

The reference for safety information for this study is the Volixibat Potassium (SHP626) Investigator's Brochure which the sponsor has provided under separate cover to all investigators.

8.2.2 Reporting Procedures

All initial and follow-up SAE reports must be reported by the investigator to the Shire Global Pharmacovigilance and Risk Management Department and the Shire GCDL within 24 hours of the first awareness of the event. Note: The 24-hour reporting requirement for SAEs does not apply to reports of abuse, misuse, overdose, or medication errors (see Section 8.1.8) unless they result in an SAE.

The investigator must complete, sign, and date the Shire Clinical Study Serious Adverse Event and Non-serious AEs Required by the Protocol Form and verify the accuracy of the information recorded on the form with the corresponding source documents (Note: Source documents are not to be sent unless requested) and fax or e-mail the form to the Shire Global Pharmacovigilance and Risk Management Department. A copy of the Shire Clinical Study Serious Adverse Event and Non-serious AEs Required by the Protocol Form (and any applicable follow-up reports) must also be sent to the Shire GCDL using the details specified in the [Emergency Contact Information](#) section of the protocol.

8.2.3 Serious Adverse Event Definition

A **Serious Adverse Event (SAE)** is any untoward medical occurrence (whether considered to be related to the IP or not) that at any dose:

- Results in death
- Is life-threatening. Note: The term 'life-threatening' in the definition of "serious" refers to an event in which the subject was at risk of death at the time of the event; it does not refer to an event which hypothetically might have caused death if it was more severe.
- Requires inpatient hospitalization or prolongation of existing hospitalization. Note: Hospitalizations, which are the result of elective or previously scheduled surgery for pre-existing conditions, which have not worsened after initiation of treatment, should not be classified as SAEs. For example, an admission for a previously scheduled ventral hernia repair would not be classified as an SAE; however, complication(s) resulting from a hospitalization for an elective or previously scheduled surgery that meet(s) serious criteria must be reported as SAE(s).
- Results in persistent or significant disability/incapacity
- Is a congenital abnormality/birth defect

- Is an important medical event. Note: Important medical events that may not result in death, be life-threatening, or require hospitalization may be considered an SAE when, based upon appropriate medical judgment, they may jeopardize the subject and may require medical or surgical intervention to prevent 1 of the outcomes listed in this definition. Examples of such medical events include allergic bronchospasm requiring intensive treatment in an emergency room or at home; blood dyscrasias or convulsions that do not result in inpatient hospitalization; or the development of drug dependency or drug abuse.

All SAEs (regardless of relationship to study) are collected from the time the subject signs the informed consent until the defined follow-up period stated in Section 7.1.4, and must be reported to the Shire Global Pharmacovigilance and Risk Management Department and the Shire GCDL within 24 hours of the first awareness of the event.

In addition, any SAE(s) considered “related” to the IP and discovered by the investigator at any interval after the study has completed must be reported to the Shire Global Pharmacovigilance and Risk Management Department within 24 hours of the first awareness of the event.

8.2.4 Serious Adverse Event Onset and Resolution Dates

The onset date of the SAE is defined as the date the event meets serious criteria. The resolution date is the date the event no longer meets serious criteria, the date the symptoms resolve, or the event is considered chronic. In the case of hospitalizations, the hospital admission and discharge dates are considered the onset and resolution dates, respectively.

In addition, any signs or symptoms experienced by the subject after signing the informed consent form, or leading up to the onset date of the SAE, or following the resolution date of the SAE, must be recorded as an AE, if appropriate.

8.2.5 Fatal Outcome

Any SAE that results in the subject’s death (ie, the SAE was noted as the primary cause of death) must have fatal checked as an outcome with the date of death recorded as the resolution date. For all other events ongoing at the time of death that did not contribute to the subject’s death, the outcome should be considered not resolved, without a resolution date recorded.

For any SAE that results in the subject’s death or any ongoing events at the time of death, unless another IP action was previously taken (eg, drug interrupted, reduced, withdrawn), the action taken with the IP should be recorded as “dose not changed” or “not applicable” (if the subject never received the IP). The IP action of “withdrawn” should not be selected solely as a result of the subject’s death.

8.2.6 Regulatory Agency, Institutional Review Board, Ethics Committee, and Site Reporting

The CRO is responsible for notifying the relevant regulatory authorities as appropriate: USA central IRBs/EU central ECs of related, unexpected SAEs.

In addition the CRO is responsible for notifying active sites of all related, unexpected SAEs occurring during all interventional studies across the SHP626-201 program.

The investigator is responsible for notifying the local IRB, local EC, or the relevant local regulatory authority of all SAEs that occur at his or her site as required.

9. DATA MANAGEMENT AND STATISTICAL METHODS

9.1 Data Collection

The investigators' authorized site personnel must enter the information required by the protocol on the eCRF. A study monitor will visit each site in accordance with the monitoring plan and review the eCRF data against the source data for completeness and accuracy. Discrepancies between source data and data entered on the eCRF will be addressed by qualified site personnel. When a data discrepancy warrants correction, the correction will be made by authorized site personnel. Data collection procedures will be discussed with the site at the site initiation visit and/or at the investigator's meeting. Once a subject is randomized, it is expected that site personnel will complete the eCRF entry within approximately 3 business days of the subject's visit.

9.2 Clinical Data Management

Data are to be entered into a clinical database as specified in the CRO's data management plan. Quality control and data validation procedures are applied to ensure the validity and accuracy of the clinical database.

Data are to be reviewed and checked for omissions, errors, and values requiring further clarification using computerized and manual procedures. Data queries requiring clarification are to be communicated to the site for resolution. Only authorized personnel will make corrections to the clinical database, and all corrections are documented in an auditable manner.

9.3 Data Handling Considerations

Data that may potentially unblind the treatment assignment (ie, IP serum concentrations, antibiotics to investigation product, treatment allocation, and IP preparation/accountability data) will be handled with special care during the data cleaning and review process. These data will be handled in such a way that, prior to unblinding, any data that may unblind study team personnel will be presented as blinded information or otherwise will not be made available. If applicable, unblinded data may be made available to quality assurance representatives for the purposes of conducting independent drug audits.

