6.2.2 Allocation of Subjects to Treatment

This is a double-blind, PBO-controlled study. The actual treatment given to individual subjects is determined by a randomization schedule.

Subject numbers are assigned to all subjects as they consent to take part in the study. Within each site (numbered uniquely within a protocol), the subject number is assigned to subjects according to the sequence of presentation for study participation.

The randomization number represents a unique number corresponding to the IP allocated to the subject, once eligibility has been determined.

Individual subject treatment is automatically assigned by the IRT.

Once a randomization number/unique identifier has been assigned, that number must not be used again if, for example, a subject is withdrawn from the study. If a randomization number/unique identifier is allocated incorrectly, the clinical research associate (CRA)/study monitor must be notified as soon as the error is discovered.

IP packaging identification numbers, separate from randomization numbers/unique identifiers, may also be assigned to subjects for specific treatment assignment as dictated by the study. In these cases, the same IP packing identification number may not be assigned to more than 1 subject.

Subjects will be equally allocated to all volixibat doses and PBO if their randomization precedes the 24 week IA. If a subject's randomization occurs after the 24 week IA, subjects will be equally allocated to all remaining volixibat doses (determined based on the results of the IA) and PBO. The randomization will be stratified by baseline T2DM and NAS ≥ 6 or NAS = {4, 5}.

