7.2.3.5 Clinical Laboratory Evaluations

All clinical laboratory assays will be performed according to the central laboratory's normal procedures. Reference ranges supplied by the central laboratory will be used to assess the clinical laboratory data for clinical significance and out-of-range pathological changes. The investigator should assess out-of-range clinical laboratory values for clinical significance, indicating if the value(s) is/are not clinically significant or clinically significant. Clinically significant findings should be evaluated for recording as adverse events on the eCRF. Abnormal clinical laboratory values, which are unexpected or not explained by the subject's clinical condition, may, at the discretion of the investigator or sponsor, be repeated as soon as possible until confirmed, explained, or resolved.

The following clinical laboratory assessments will be performed:

Biochemistry

- Albumin (ALB)
- Alkaline phosphatase (ALP)
- Alanine aminotransferase (ALT; SGPT)
- Aspartate aminotransferase (AST; SGOT)
- Blood urea nitrogen (BUN)
- C4
- Calcium (Ca)
- Bicarbonate (CO₂)
- Chloride (Cl)
- Creatinine
- Creatine kinase
- Gamma glutamyl transferase (GGT)
- Glucose
- Lactate dehydrogenase (LDH)
- Magnesium (Mg)
- Phosphate (P)
- Potassium (K)
- Sodium (Na)
- Total and direct bilirubin
- Total cholesterol
- Protein
- Triiodothyronine (T₃)
- Thyroid-stimulating hormone (TSH)
- Triglycerides
- Uric acid

Hematology

- Hemoglobin
- Hematocrit
- Mean corpuscular hemoglobin (MCH)
- Mean corpuscular volume (MCV)
- Platelets
- Red blood cell (RBC)
- White blood cell (WBC) count with differential
- Prothrombin time (PT)
- Activated partial thromboplastin time (aPTT)
- International normalized ratio (INR)

Urinalysis

- Appearance (clarity and color)
- Bilirubin
- Blood
- Glucose
- Ketones
- Leukocyte esterase
- Microscopic examination of sediment
- Nitrite
- pH
- Protein
- Specific gravity
- Urobilinogen
- Oxalate

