7.2.3.6 Additional Laboratory Assessments

Laboratory samples will be collected and assessed for:

- HIV testing and assessment of Hepatitis B/C including HBcAb, HBsAg, HBVDNA, and HCVA_b, and HCVRNA will occur at the screening visit only
- Lipid panel including fasting total cholesterol, HDL-C, LDL-C, and triglycerides at each scheduled study visit (Visits 1 through 10)
- HbA1c will be tested at every scheduled visit (Visits 1 through 10)
- Full coagulation panel will be done at screening and baseline, but only PT/INR is required at remaining time points at Visits 4, 7, and 9
- Insulin will be tested at screening, baseline, at Visit 4 and Visits 6 through 10
- HOMA-IR and HOMA-%B: will be calculated programmatically from serum glucose tested at screening, baseline, Visits 7, 9, and 10

- Vitamin A, Vitamin D, Vitamin E, and Vitamin K (via PT/INR) will be tested at screening, baseline, and Visits 4, 7, and 9
- Thyroid testing including TSH and T3 will be tested at screening, baseline, and Visits 4, 6, 7, 9, and 10
- C4 samples will be collected at baseline and Visits 6, 7, 9, and 10

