One of the factors contributing to the pathogenesis of NASH is abnormal cholesterol metabolism and the accumulation of free cholesterol in the liver. The free cholesterol is directly toxic to hepatocytes, which leads to inflammation and fibrosis (Musso et al. 2013). One treatment approach is to remove the cholesterol from the liver to decrease and possibly reverse the damage to the hepatocytes. This is one of the mechanisms by which SHP626 will treat NASH.

Due to the mechanism of action (MOA), volixibat is under development for the treatment of NASH and may also be able to improve the metabolic syndrome that is associated with NASH. Volixibat inhibits ASBT therefore BAs are excreted in the feces and this loss forces the liver to synthesize new BA which utilizes cholesterol in the liver and serum. Volixibat also has the potential to reduce IR, which is considered to be the most common underlying risk factor for the development of NASH (Pagano et al. 2002; Sanyal et al. 2001).

Volixibat was initially being evaluated for its use as an intervention for dyslipidemia. As a result of initial observations in animals that serum low-density lipoprotein cholesterol (LDL-C) and total liver cholesterol content could be decreased after administration of volixibat, additional work was undertaken to support the safety and tolerability of the drug in healthy volunteers. Clinical and non-clinical studies have demonstrated very low systemic exposure across species. Oral administration of volixibat at doses up to 300 mg once daily and 50 mg administered daily for 14 days to healthy male subjects was generally safe. A Phase 1 study revealed that volixibat is tolerated at the 10 mg dose for 28 days and that there were trends towards increasing high-

density lipoprotein cholesterol (HDL-C), decreasing LDL-C, and decreasing fasting glucose in patients with T2DM (LUM002-101 trial).

A healthy volunteer study investigating 12 days of varying levels of repeat doses of volixibat has provided key pharmacodynamic information for dose selection as measured by the effect of volixibat on excreted fecal bile acid (FBA) levels (SHP626-101). In addition, the study investigated safety and tolerability over the dose range that was considered for this Phase 2 study.

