2.2.3 Exploratory Objectives

- To explore the effect of volixibat compared to PBO on liver histology (measured by individual SAF scoring components: Steatosis (S), Activity (A), and Fibrosis (F))
- To explore the effect of volixibat compared to PBO on anthropometric measures (body weight, body mass index (BMI), waist circumference and waist-hip ratio)
- To explore the effect of volixibat compared to PBO on homeostasis model assessment 2-IR (HOMA2-IR) and HOMA2-beta cell function (HOMA2-%B) in subjects with T2DM
- To explore the effect of volixibat compared to PBO on BA synthesis (7-alpha-hydroxy-4-cholesten-3-one [C4])

- To explore the effect of volixibat on patient-reported health-related quality of life (HRQoL) and overall health status.

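### C4, the trial's marker of bile-acid synthesis, sits in the investigator-reviewed laboratory panel and is missing from the Section 9.3 list of unblinding data, so on-treatment results may let allocation be inferred

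*Protocol*

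**What the plan says.** The trial is masked. Section 6.2.2 states: "This is a double-blind, PBO-controlled study".

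- **Section 7.2.3.5** lists C4 under Biochemistry among the central laboratory assessments. It adds: "The investigator should assess out-of-range clinical laboratory values for clinical significance". Clinically significant findings are then considered as adverse events.
- **Section 7.2.3.6** fixes the timing: "C4 samples will be collected at baseline and Visits 6, 7, 9, and 10". By Section 7.1.3, Visits 6, 7 and 9 are Weeks 12, 24 and 48. Visit 10 is the Week 52 follow-up.
- **Section 9.3** names the data that need special care: "Data that may potentially unblind the treatment assignment (ie, IP serum concentrations, antibiotics to investigation product, treatment allocation, and IP preparation/accountability data". C4 is not among them.
- **Section 1.2** (Amendment 1 text in the same file; the current Section 1 is not shown) says of bile-acid loss on the drug that "this loss forces the liver to synthesize new BA which utilizes cholesterol in the liver and serum". Section 2.2.3 of that version names C4 as the measure of bile-acid synthesis.

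**The concern.** A pharmacodynamic marker that responds to the drug and not to placebo can weaken a blind as a drug concentration can. Section 9.3 guards against concentrations but not against C4.

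What is at stake is mainly what the investigator judges:

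- Relatedness of each adverse event (Section 8.1.2).
- Whether a subject stops because of a TEAE. Section 9.5.1 compares these discontinuations between each dose and placebo to assess tolerability at the interim, where doses are dropped.
- Indirectly, the primary endpoint. Section 7.1.3 requires no final biopsy from subjects who discontinue before Week 44, so withdrawals influenced by a guess at allocation would leave Week 48 histology missing unequally between arms.

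**Working it through.** The protocol gives no figure on this point to reproduce. The check is a reading of the text, followed by an illustration under stated assumptions.

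**1. Is C4 within the investigator's review?** Section 7.2.3.5 names it in the panel and gives the review duty without exempting it. Section 8.1.5 adds that an on-treatment shift from normal to abnormal can represent an adverse event, and that values newly abnormal at the end of treatment should be investigated. Read literally, both duties cover C4 and presuppose that the site sees the result.

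**2. Should C4 differ between arms?** The Amendment 1 background says the drug drives new bile-acid synthesis, and its objectives make C4 the measure of that synthesis. The current Sections 7.2.3.5 and 7.2.3.6 still collect C4, so the direction of effect follows from the stated mechanism. The size does not.

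**3. Does Section 9.3 catch it?**

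| Item | In the Section 9.3 list | Among the assessments in Sections 7.2.3.5 and 7.2.3.6 |
|---|---|---|
| IP serum concentrations | yes | no (Amendment 1, Section 1.2: no pharmacokinetic sampling) |
| The item printed as antibiotics to the product | yes | no |
| C4 | no | yes |

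The remaining two list items, treatment allocation and IP preparation or accountability, are administrative.

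**4. Which results can matter?** Week 12 precedes each subject's Week 24 interim visit. Weeks 12 and 24 both precede the biopsy. The Week 48 sample is taken at the end-of-study visit, when the biopsy is due, and Week 52 is later, so neither can cause withdrawal or biopsy loss. Discontinuations before Week 12 are untouched.

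**5. How informative might one reading be?** The documents give neither an effect size nor an SD. I assume two normal distributions of equal variance, active and placebo, separated by *d* SD, with all doses pooled as active. Before the interim, "Subjects will be equally allocated to all volixibat doses and PBO if their randomization precedes the 24 week IA", so three of four subjects are on active drug: *p* = 0.75. If two doses continue afterwards, *p* = 2/3.

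- AUC = Φ(*d*/√2)
- Best cut-off *t* = *d*/2 − ln[*p*/(1−*p*)]/*d*
- Proportion guessed correctly = *p*·Φ(*d*−*t*) + (1−*p*)·Φ(*t*)

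For *d* = 2 and *p* = 0.75: *t* = 1 − 1.0986/2 = 0.451, and 0.75·Φ(1.549) + 0.25·Φ(0.451) = 0.75·0.939 + 0.25·0.674 = 0.873.

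| Assumed *d* (SD) | AUC | Correct at 3:1 | Correct at 2:1 |
|---|---|---|---|
| 0 (always guess active) | 0.50 | 75.0% | 66.7% |
| 0.5 | 0.64 | 75.1% | 67.5% |
| 1 | 0.76 | 77.7% | 73.0% |
| 1.5 | 0.86 | 82.5% | 79.6% |
| 2 | 0.92 | 87.3% | 85.5% |
| 3 | 0.98 | 94.5% | 93.8% |

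Below about 1 SD a single reading says little about an individual. At 2 SD or more it would materially weaken the blind.

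**The case against.** The strongest case against has five parts.

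- **Reporting route.** No sentence says C4 results go to sites. The panel in Section 7.2.3.5 may be only an inventory: it also holds TSH and T3, which Section 7.2.3.6 schedules separately, and the Amendment 1 Table 1 gives C4 its own row. A laboratory manual or data management plan could mask it. This stands as a limit on certainty. It does not remove the point, because masking set out elsewhere would sit awkwardly with review duties that make no exception for C4.
- **General wording in Section 9.3.** Its last part says data that may unblind study team personnel will be masked or withheld, which could be read to include C4. That reading is arguable for sponsor and CRO staff. However, the sentence refers back to the listed data and concerns data cleaning and review, not laboratory reports to investigators.
- **Boilerplate.** The list looks generic, so its *ie* may not have been meant as exhaustive. That explains the omission but does not cure it.
- **Other cues.** Section 9.5.1 expects gastrointestinal events on the drug, and lipids, which the same mechanism would move, are measured at every visit (Section 7.2.3.6). Masking C4 leaves these in place. This is true, but disclosure of C4 is the avoidable part.
- **Subject-reported outcomes.** EQ-5D and stool assessments would be affected only if subjects learned their C4 results, and nothing says they would.

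A reader might infer that investigators and the sponsor can tell who is on active drug, or that the primary result is biased. The documents support neither: there is no C4 effect size, no stated reporting route to sites, and histology is read centrally (Amendment 1 synopsis and Table 1 footnote).

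**Conclusion.** The point holds as a gap in the masking provisions, not as a demonstrated unblinding. Followed as written, Sections 7.2.3.5 and 9.3 would let sites and the study team see a pharmacodynamic marker at Weeks 12 and 24, and allocation *may* be inferred from it.

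The outcomes exposed are adverse event relatedness, attribution of discontinuations to TEAEs and, through withdrawal, completeness of the Week 48 biopsy. The size cannot be fixed from the documents. Across assumed separations of 0.5 to 3 SD, the gain over always guessing active at 3:1 runs from 0.1 to 19.5 percentage points (75.1 − 75.0 and 94.5 − 75.0).

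The conclusion assumes that the current protocol keeps the mechanism and the role of C4 given in Amendment 1, that C4 is reported like the rest of its panel, and that the histology reader does not see laboratory data. It is a cheap improvement.

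**What to change.** 1. Add C4 to the list in Section 9.3.
2. Remove C4 from the site-reviewed biochemistry panel in Section 7.2.3.5, keeping its sampling schedule in Section 7.2.3.6.
3. State that the central laboratory withholds all post-baseline C4 results from sites, the CRO and the sponsor study team until database lock, with earlier release only to the independent statistician and the DMC.

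The cost is a reporting flag at the central laboratory and a few lines of protocol text. The downside is that sites cannot review C4 during treatment; the document states no safety threshold for it. The change does not remove gastrointestinal or lipid cues and should not be presented as doing so.
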